01/15/2021	8	
Addition of rapid antigen test for screening.
 
Addition of social media advertising and other forms of advertising for recruitment.
 
Addition of payment \$50 per subject.
 
Updated risks of Nasopharyngeal swabs.
	

FUNDING:

Indicate any funding for this proposal. This should match the Funding Sources page in Click IRB.

Response: SUNY SEED

GRANT APPLICABILITY:

Indicate whether this protocol is funded by a grant (e.g. NIH, foundation grant). For a grant with multiple aims, indicate which aims are covered by this research proposal.

NOTE: This question does not apply to studies funded by a sponsor contract.

Include a copy of the grant proposal with your submission.

Response: SUNY SEED

RESEARCH REPOSITORY:

Indicate where the research files will be kept, including when the study has been closed. The repository should include, at minimum, copies of IRB correspondence (approval, determination letters) as well as signed consent documents. This documentation should be maintained for 3 years after the study has been closed.

Response: All study approval documents and correspondence that is not stored in the Click System will be retained in the office of [name].

Location: Jacobs School of Medicine and Biomedical Science, Suite 3212

Address: [name]

Department: Pharmacology and Toxicology

1.0 Study Summary

Study Title	A pilot placebo-controlled randomized double-blind trial of Melatonin in outpatients with COVID infection.
Study Design	This study is a pilot randomized, double-blind, placebo-controlled clinical trial to evaluate the safety and efficacy of melatonin in outpatient adult patients suspected to be afflicted with COVID-19.
Primary Objective	Evaluate the safety of the intervention through 42 days of follow-up as compared to the control arm as assessed by: 
• Cumulative incidence of serious adverse events (SAEs)• Cumulative incidence of Grade 3 and 4 adverse events (AEs).• Adverse Events of Special Interest• Discontinuation or temporary suspension of the investigational medication (for any reason).
Secondary Objective(s)	Evaluate the clinical efficacy of melatonin as compared to placebo as assessed by: Hospitalization Incidence of COVID related hospitalization at 42 days. Data will be obtained from electronic medical record. COVID related symptoms The speed of resolution of COVID related symptoms Change from baseline Day 1 to Day 42. Change in the WHO Clinical Progression Scale (0-10). Data will be obtained from electronic medical record. Mortality 42-day mortality. Data will be obtained from electronic medical record.

Research Intervention(s)/Investigational Agent(s)	Melatonin (5-methoxy-N-acetyl tryptamine)
IND/IDE #	150700
Study Population	Outpatient adult (≥ 18 years old) patients with COVID-19.
Sample Size	30 subjects
Study Duration for individual participants	42 days
Study Specific Abbreviations/Definitions	COVID-19: Coronavirus Disease 2019

2.0 Objectives*

2.1 Describe the purpose, specific aims, or objectives of this research.

Response: The study is designed to evaluate the safety and efficacy of Melatonin. Participants will be enrolled as outpatients within 5 days of positive COVID-19 test. The ultimate goal is to determine in an adequately powered study if the anti-inflammatory and antioxidant actions of Melatonin can reduce the severity and prevent progression of COVID when started in mild disease.

2.2 State the hypotheses to be tested, if applicable.

NOTE: A hypothesis is a specific, testable prediction about what you expect to happen in your study that corresponds with your above listed objectives.

Response: Melatonin reduces inflammation and oxidative stress in COVID-19 patients reducing the severity of the disease.

3.0 Scientific Endpoints*

2.1 Describe the scientific endpoint(s), the main result or occurrence under study.

*NOTE: Scientific endpoints are outcomes defined before the study begins to determine whether the objectives of the study have been met and to draw conclusions from the data. Include primary and secondary endpoints. Some example endpoints are: reduction of symptoms, improvement in quality of life, or survival. Your response should **not** be a date.*

Response:

Primary Objective

Evaluate the safety of the intervention through 42 days of follow-up as compared to the control arm as assessed by:

- Cumulative incidence of serious adverse events (SAEs)
- Cumulative incidence of Grade 3 and 4 adverse events (AEs).

- Adverse Events of Special Interest
- Discontinuation or temporary suspension of the investigational medication (for any reason).

Secondary Objectives

Evaluate the clinical efficacy of melatonin as compared to placebo as assessed by:

Hospitalization: Incidence of COVID related hospitalization at 42 days.

Data will be obtained from electronic medical record.

COVID related symptoms: Fever, chills, cough, nasal symptoms, body aches/muscle aches, headache, loss of smell, loss of taste, nausea, vomiting, diarrhea, fatigue, dizziness. The speed of resolution of COVID related symptoms. Change from baseline, Day 1 to Day 42. Accessed by questionnarre.

Change in the WHO Clinical Progression Scale (0-10). Data will be obtained from electronic medical record.

Mortality: 42-day mortality. Data will be obtained from electronic medical record.

Exploratory Objective

Evaluate the effect of melatonin on virologic parameters as compared to placebo and assessed by:

-Percent of subjects with SARS-CoV-2 detectable in saliva sample at days 1, 3, 7, 14, 28 and 42.

-Quantitative RT-PCR for SARS-CoV-2 virus in saliva sample at days 1, 3, 7, 14, 28 and 42.

-Evaluate the reduction in cytokine/chemokine RNA and/or protein levels in saliva:

-Reduction as compared to baseline (Day 1) in salivary levels of cytokine/chemokine RNA and/or protein (IL-1, IL-2, IL-3, IL-4, IL-6, IL-8, IL-10, IL-11, IL-12, IL-13, IL-17, IL-18, TNF α , IFNy, IFN α , IFN-B, MCP1) at days 3, 7, 14, and 28.

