8.0 Inclusion and Exclusion Criteria*

8.1 *Describe the criteria that define who will be **included** in your final study sample.*

NOTE: This may be done in bullet point fashion.

Response:

- a. Male or non-pregnant female adult ≥ 18 years of age at time of enrolment.
- b. Women of childbearing potential must agree to use at least one primary form of contraception for the duration of the study.
- c. Onset of COVID-19 Symptoms within 5 days
- d. Positive testing for COVID-19 infection by standard RT-PCR assay or equivalent test within 5 days or willingness to receive a rapid antigen test (EUA Nasal swab antigen test) by the study team. Following enrollment, among subjects that have not received a COVID test yet or its results, a nasopharyngeal swab sample will be obtained and a rapid antigen test (**CareStart™ COVID-19 Antigen Test**) by the study team.
- e. Meets criteria for mild or moderate COVID disease defined as follows:
Mild COVID-19
 - Symptoms of mild illness with COVID-19 that could include fever, cough, sore throat, malaise, headache, muscle pain, gastrointestinal symptoms, without shortness of breath or dyspnea
 - No clinical signs indicative of Moderate, Severe, or Critical Severity**Moderate COVID-19**
 - Symptoms of moderate illness with COVID-19, which could include any symptom of mild illness or shortness of breath with exertion
 - Clinical signs suggestive of moderate illness with COVID-19, such as respiratory rate ≥ 20 breaths per minute, saturation of oxygen (SpO_2) $> 93\%$ on room air at sea level, heart rate ≥ 90 beats per minute.
 - No clinical signs indicative of Severe or Critical Illness Severity
- f. Subject provides written informed consent prior to initiation of any study procedures.
- g. Understands and agrees to comply with planned study procedures.
- h. Agrees to the collection and storage of saliva samples per protocol.
- i. Subject agrees to provide an emergency contact who the study team can contact in case the subject is not reachable on any of the study visits

8.2 *Describe the criteria that define who will be **excluded** from your final study sample.*

NOTE: This may be done in bullet point fashion.

Response:

- a. Severe chronic kidney disease ($eGFR < 30$ ml/min) or Moderate renal impairment ($eGFR 30-60$ ml/min) or requiring dialysis

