- b. Severe hepatic insufficiency defined as one or more of the following: Cirrhosis diagnosis, Serum ALT $> 3x$ ULN or Alkaline phosphatase $> 3x$ ULN or bilirubin $> 2x$ ULN in the absence of Gilbert's or hemolysis, Uncontrolled acute or chronic liver disease (e.g. acute hepatitis A, unstable autoimmune hepatitis)
- c. Pregnancy or breast feeding.
- d. History of a seizure disorder.
- e. Patient is taking Fluvoxamine, Capmatinib, Ciprofloxacin (Systemic),

Deferasirox, Givosiran, Methoxsalen (Systemic), Mexiletine, Rucaparib, Stiripentol, Thiabendazole, Vemurafenib, Methoxsalen, Sodium oxybate or Echinacea.

- f. Allergy to the study medication
- g. Currently taking melatonin
- h. Currently taking high dose (>500 mg/day) Vitamin C.
- i. Meets criteria for Severe or Critical COVID-19 infection defined as follows:

Severe COVID-19

- Symptoms suggestive of severe systemic illness with COVID-19, which could include any symptom of moderate illness or shortness of breath at rest, or respiratory distress
- Clinical signs indicative of severe systemic illness with COVID-19, such as respiratory rate ≥ 30 per minute, heart rate ≥ 125 per minute, $\text{SpO}_2 \leq 93\%$ on room air at sea level or $\text{PaO}_2/\text{FiO}_2 < 300$
- No criteria for Critical Severity

Critical Covid-19

- Evidence of critical illness, defined by at least one of the following:
 - Respiratory failure defined based on resource utilization requiring at least one of the following:
 - Endotracheal intubation and mechanical ventilation, oxygen delivered by high-flow nasal cannula (heated, humidified, oxygen delivered via reinforced nasal cannula at flow rates > 20 L/min with fraction of delivered oxygen ≥ 0.5), noninvasive positive pressure ventilation, ECMO, or clinical diagnosis of respiratory failure (i.e., clinical need for one of the preceding therapies, but preceding therapies not able to be administered in setting of resource limitation)
 - Shock (defined by systolic blood pressure < 90 mm Hg, or diastolic blood pressure < 60 mm Hg or requiring vasopressors)
 - Multi-organ dysfunction/failure

8.3 *Indicate specifically whether you will include any of the following special populations in your study using the checkboxes below.*

NOTE: Members of special populations may not be targeted for enrollment in your study unless you indicate this in your inclusion criteria.

Response:

- Adults unable to consent
- Individuals who are not yet adults (infants, children, teenagers)

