12.0 Procedures Involved*

12.1 Provide a description of *all research procedures or activities* being performed and when they are performed once a subject is screened and determined to be eligible. Provide as much detail as possible.

NOTE: This should serve as a blueprint for your study and include enough detail so that another investigator could pick up your protocol and replicate the research. For studies that have multiple or complex visits or procedures, consider the addition of a schedule of events table in in your response.

Response: Because of the highly contagious nature of COVID infection in the first few days after onset of symptoms, it is essential to minimize exposure of research team members to the subjects. Therefore, except for the enrollment visit, all procedures for this study will be conducted remotely at the subject's home. The Table below depicts all the research procedures.

	Screen	Enrollment							
Day +/- Window	-1 or 1	1	Daily until	Daily until	Day 3 ± 1	Day 7 ± 1	Day 14 ± 2	Day 28 ± 3	Day 42 ± 3

			day 14	day 42					
Assessments/Procedures									
ELIGIBILITY									
Informed consent	X								
Demographics & Medical History	X								
Prior SARS-CoV-2 based on screening or perform rapid antigen testing	X								
STUDY INTERVENTION									
Randomization		X							
Administration of Melatonin/Placebo		X	X						
STUDY PROCEDURES									
Body temperature		X	X	X	X	X	X	X	X
Clinical data collection		X	X	X	X	X	X	X	X
Pulse Oximetry measurement		X	X	X	X	X	X	X	X
Adverse event evaluation		X			X	X	X	X	X
RESEARCH LABORATORY									
Saliva for PCR SARS-CoV-2		X			X	X	X	X	X
Saliva for Cytokine/Chemokine RNA and/or protein		X			X	X	X	X	X

Below is a day by day description of the study procedures.

- For those subjects that have not had a COVID-test: Subjects will be enrolled and then tested for SARS-CoV2 using an EUA rapid antigen administered by the study team. If negative by rapid antigen test subjects will be withdrawn from study. Those subjects that have a prior positive test will not be give a rapid antigen test.
- If COVID-19 positive:
- Collect a baseline sample of saliva prior to taking drug, by spitting in a collection container that will be provided at time of consent.
- Rate COVID symptoms before starting medication and then each day in the evening on a short questionnaire from Day 1 to Day 42.
- Record body temperature and pulse oximetry each day in the morning and evening.

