Statistical analyses: Analyses will be performed with a focus on estimation of specific clinically important parameters, including preliminary evidence of safety and activity of the intervention, for use in the planning of subsequent comparative trials designed to fully assess safety and efficacy. The primary outcomes in the examination of the study intervention, specifically, the cumulative incidence of serious adverse events (SAEs), the cumulative incidence of Grade 3 and 4 adverse events (AEs), and the discontinuation or temporary suspension of the investigational medication (for any reason), are measured in a binary fashion at the

study participant-level. The corresponding probabilities will each be estimated using the relative frequency. In addition to the point estimates based on collected data, 95% confidence intervals will also be computed based on the methodology of Clopper and Pearson. Additional binary study outcomes, ex., incidence of COVID-related hospitalization and hospitalization for any reason, will be analyzed in an identical fashion. Comparison between randomized groups with regards to these outcomes will be done using Fisher's exact test. For numeric outcomes, such as symptom questionnaire results and measures of clinical improvement, the rank-based Wilcoxon rank sum test will be used to compare groups. For outcomes which may be subject to censoring such as speed of resolution of COVID related symptoms, parameter estimation will be based on the Kaplan-Meier estimator and the log-rank test will be utilized to compare groups. Proposed exploratory outcomes are collected longitudinally. Proposed exploratory outcomes are collected longitudinally. Standard statistical techniques for the analysis of such outcomes, ex., mixed linear models, will be utilized. Although primary analyses will be performed based on the intent-to-treat principle, to evaluate the robustness of these results, analyses will also be conducted in a secondary fashion based on actual treatment received. All statistical tests will be two-sided and tested at a 0.05 nominal significance level. All analyses will be carried out using SAS version 9.4 (or higher) statistical software (Cary, NC).

19.2 *If applicable, provide a power analysis.*

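### The symptom list for the secondary resolution endpoint omits shortness of breath and sore throat, which the entry criteria use, so a still-breathless subject could be counted as resolved if the list is applied as written

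*Combined protocol and SAP*

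**What the plan says.** All references are to the combined protocol and SAP.

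- **Endpoint (section 3.0, Secondary Objectives).** The symptoms are "Fever, chills, cough, nasal symptoms, body aches/muscle aches, headache, loss of smell, loss of taste, nausea, vomiting, diarrhea, fatigue, dizziness". Nothing in the wording marks the list as a set of examples. The measure is "The speed of resolution of COVID related symptoms. Change from baseline, Day 1 to Day 42", assessed by questionnaire.
- **Data source (section 12.1).** Subjects rate symptoms before the first dose and then "each day in the evening on a short questionnaire from Day 1 to Day 42". Section 12.3 names the form as a submitted attachment; it is not reproduced.
- **Entry criteria (section 8.1, criterion e).** Mild disease may show, among other symptoms, "sore throat, malaise, headache, muscle pain, gastrointestinal symptoms, without shortness of breath or dyspnea". Moderate disease has symptoms "which could include any symptom of mild illness or shortness of breath with exertion". Both groups are eligible.
- **Exclusion criteria (section 8.2, criterion i).** Severe disease has symptoms "which could include any symptom of moderate illness or shortness of breath at rest, or respiratory distress".
- **Analysis (section 19.1).** "For outcomes which may be subject to censoring such as speed of resolution of COVID related symptoms", the plan uses Kaplan-Meier estimates and a log-rank test. Numeric questionnaire results are compared by the Wilcoxon rank sum test. No section says when a subject counts as resolved.

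**The concern.** The symptoms that bring a subject into the trial and the symptoms that are timed to resolution should match, or the difference should be explained. Here they differ on two symptoms. One of them, breathlessness, is the symptom that the protocol itself grades from mild through moderate to severe disease.

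At stake is the meaning of the only patient-reported efficacy endpoint. Section 19.1 says that the estimates are meant to help plan later comparative trials. A resolution time that ignores breathlessness would therefore be carried forward. Daily symptom ratings that were never collected cannot be reliably recovered afterwards.

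**Working it through.** **Plan's own figure.** The documents give no number for this endpoint. The only sample-size figure (section 19.2) is a standard error of at most 11 percentage points for a safety proportion with 20 subjects: sqrt(0.5 × 0.5 / 20) = 0.1118, or 11.2 points, which agrees on rounding. It does not depend on the symptom list, so changing the list leaves the sample size as it is.

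**Step 1: set the lists side by side.** The symptoms named for mild and moderate disease in section 8.1, against the 13 items in section 3.0:

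| Entry symptom (8.1) | Item in 3.0 |
|---|---|
| Fever | Fever |
| Cough | Cough |
| Headache | Headache |
| Muscle pain | Body or muscle aches |
| Gastrointestinal symptoms | Nausea, vomiting, diarrhea |
| Malaise | Fatigue (nearest item) |
| Sore throat | None |
| Breathlessness on exertion | None |

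Six of the eight are covered, counting fatigue for malaise, and 8 − 6 = 2 are not.

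**Step 2: follow the list into the analysis.** Since resolution is undefined, take the plausible readings in turn.

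- *All listed symptoms absent.* A subject with moderate disease whose 13 items have cleared, but who is still breathless on exertion, has the event. A subject who entered with sore throat alone, or breathlessness on exertion alone, has no listed symptom at baseline. That subject is either resolved from the start or has no event to time.
- *All listed symptoms that were present at baseline absent.* The still-breathless subject again has the event. The subject with only an unlisted symptom drops out of the analysis.
- *Symptom by symptom.* Nobody is misclassified, but no resolution curve exists for breathlessness or sore throat.

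Each reading loses something, although not the same thing.

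**Step 3: change from baseline.** If the 13 items do not change, a subject who becomes breathless shows no worsening on any score built from them.

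**Step 4: look for the symptom elsewhere.**

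- Oximetry is recorded twice daily (section 12.1). The moderate definition in section 8.1 itself lists saturation above 93%, so oximetry need not reveal breathlessness on exertion.
- The WHO scale, hospitalization and mortality come from the medical record (section 3.0). Breathlessness managed at home may never reach that record.
- Adverse events are asked about at enrollment and on Days 3, 7, 14, 28 and 42, not daily.

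None of these is part of the resolution event in section 19.1.

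**The case against.** The strongest reply is that subjects complete a form, not section 3.0, and the form is not available here. It may already ask about both symptoms. This stands: the documents establish what the endpoint definition leaves out, not what is collected. If the form does hold the items, section 3.0 and the form disagree and still have to be reconciled.

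Second, no rule for resolution or for a total score is written, so any example of a misclassified subject supplies a rule of its own. This also stands, and it is why the consequence is worded as possible. It does not remove the point, because each reading above loses information on the omitted symptoms.

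Third, severity in sections 8.1 and 8.2 also rests on respiratory rate, heart rate and oxygen saturation. A reader might infer that breathlessness alone defines progression in this trial. The documents do not say that; it is one separating feature among several.

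Fourth, a reader might infer that the trial cannot see worsening at all. It can, in part, through oximetry, the WHO scale, hospitalization and the adverse-event calls. Section 2.1 also places the question of severity and progression in a later, adequately powered study. What remains is a gap in one secondary endpoint of a safety pilot.

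**Conclusion.** The point holds on the text: two symptoms used at entry are missing from the endpoint's list, and one of them helps to separate the grades of disease. It should be corrected, but it concerns a single secondary endpoint.

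The size cannot be given. A reader might multiply an assumed share of breathless subjects by 30. The documents give no such share. Even a known share would overstate the effect on resolution time under an all-clear rule, because that time changes only when an omitted symptom outlasts every listed one, including cough, fatigue and loss of smell or taste.

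A reader might also infer that the omission pulls the arms together. That depends on whether melatonin acts differently on breathlessness than on the listed symptoms, and nothing in the documents settles it.

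The conclusion assumes that the section 3.0 list is the full set for the endpoint, as its wording indicates. The loss of the data themselves further assumes that the unseen form follows the list.

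**What to change.** 1. Add shortness of breath (none / with exertion / at rest, matching sections 8.1 and 8.2) and sore throat to the symptom list in section 3.0.
2. Check the daily questionnaire and add the same two items if they are not already there, so that section 3.0, sections 8.1 and 8.2 and the form agree.
3. State in sections 3.0 and 19.1 that both symptoms count in the resolution event, so that a subject is not resolved while either persists.

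If the sponsor prefers to leave either symptom out, the reason should be written down.

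The cost is a short amendment and two lines on an existing self-completed form. With one rating before dosing and 42 evening ratings, that is at most 2 × 43 = 86 further entries per subject. Resolution times may become slightly longer. No visits, staff or procedures are added.

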6.0 Study Intervention/Investigational Agent

1.1 Description: *Describe the study intervention and/or investigational agent (e.g., drug, device) that is being evaluated.*

Response: Melatonin (5-methoxy-N-acetyl tryptamine)

6.1 *Drug/Device Handling: If the research involves drugs or device, describe your plans to store, handle, and administer those drugs or devices so that they will be used only on subjects and be used only by authorized investigators.*

- *If the control of the drugs or devices used in this protocol will be accomplished by following an established, approved organizational SOP (e.g., Research Pharmacy SOP for the Control of Investigational Drugs, etc.), please reference that SOP in this section.*

Response:

Melatonin is a synthetic product with white physical appearance. Melatonin is sold as a food supplement for use in humans. This study will use Melatonin Tablets (10 mg per capsules) purchased from Life Extension (Northeast Fulfillment, Inc, Edison, NJ 08837) (see certificate of analysis attached) and shipped directly to research pharmacist and stored in the research pharmacy in the CRC.

Melatonin will be administered as a 10 mg dose three times a day for 14 days. Capsules (size “4” Clear Vegetable cellulose capsule with off-white fill) containing 10 mg melatonin, microcrystalline cellulose, and rice concentrate prepared by Life Extension® (Northeast Fulfillment, Inc, Edison, NJ 08837) will be over-encapsulated in opaque gelatin capsules. Placebo capsules will be prepared with identical opaque gelatin capsules using methylcellulose. Both melatonin and placebo capsules will be given orally. Over-encapsulation of placebo and melatonin treatments will be done by the research pharmacist and will be mailed to study subjects directly by courier.

Melatonin capsules will be stored at room temperature.

Placebo capsules will be stored at room temperature.

6.2 *If the drug is investigational (has an IND) or the device has an IDE or a claim of abbreviated IDE (non-significant risk device), include the following information:*

- *Identify the holder of the IND/IDE/Abbreviated IDE.*
- *Explain procedures followed to comply with sponsor requirements for FDA regulated research for the following:*

FDA Regulation	Applicable to:		
	IND Studies	IDE studies	Abbreviated IDE studies
21 CFR 11	X	X	
21 CFR 54	X	X	
21 CFR 210	X		
21 CFR 211	X		

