- Take the IP 3 times a day orally for 14 days.
- On Days 3, 7, 14, 28 and 42 collect a sample of saliva prior to taking drug in a collection container provided. Place the sample in a collection bag and place it in a freezer.
- Speak to the research coordinator through telemedicine on Days 3, 7, 14, 28 and 42 to provide

data as well as any adverse effects of the treatment. These include anxiety and depression and drowsiness special interest adverse events. The duration of these visits will be 15-30 minutes.

- Allow a courier to come to your house to collect study related materials on Day 15 ± 3 and day 43 ± 3 to pick up study related materials.

12.2 Describe what data will be collected.

NOTE: For studies with multiple data collection points or long-term follow up, consider the addition of a schedule or table in your response.

Response: Please see Table above

12.3 List any instruments or measurement tools used to collect data (e.g. questionnaire, interview guide, validated instrument, data collection form).

Include copies of these documents with your submission.

Response: Included documents: 1) Data collection form (baseline); 2) Data collection form (Follow-up); 3) Daily symptom questionnaire; 4) Body temperature and pulse oximetry logs; 5) Instructions for saliva collection, storage and shipping 6) WHO Clinical Progression Scale

12.4 Describe any source records that will be used to collect data about subjects (e.g. school records, electronic medical records).

Response: EMR data will be accessed to ascertain baseline health information and information relevant to the participants COVID illness. The study team will have remote access to the relevant EMRs.

12.5 Indicate whether or not **individual** subject results, such as results of investigational diagnostic tests, genetic tests, or incidental findings will be shared with subjects or others (e.g., the subject's primary care physician) and if so, describe how these will be shared.

Response: No

12.6 Indicate whether or not **study** results will be shared with subjects or others, and if so, describe how these will be shared.

Response: Study results will be posted on Clinical Trials.gov and submitted for publication in a peer reviewed journal.

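### The numeric symptom score has no defined time point; read as Day 42 minus Day 1 it would have almost no sensitivity to treatment, although the planned time-to-resolution analysis would still address symptom duration

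*Combined protocol and SAP*

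**What the plan says.** Section 3.0 puts two things under one symptom heading: "The speed of resolution of COVID related symptoms. Change from baseline, Day 1 to Day 42". The Study Summary (1.0) carries the same pair, with the second part as "Change from baseline Day 1 to Day 42". Apart from "Change from baseline, Day 1 to Day 42", no day or summary is given for a symptom change score.

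Section 19.1 analyses the two parts differently. Speed of resolution is treated as a censored outcome, with Kaplan-Meier estimation and a log-rank test. For numeric outcomes, the plan names "symptom questionnaire results and measures of clinical improvement, the rank-based Wilcoxon rank sum test". It does not say which day, which summary of the daily ratings or which score enters that test, and it includes no baseline adjustment.

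The data are richer than the endpoint line suggests. Section 12.1 asks subjects to "Rate COVID symptoms before starting medication and then each day in the evening on a short questionnaire from Day 1 to Day 42". Dosing is "three times a day for 14 days" (6.1, and likewise 12.1). Subjects are outpatients with mild or moderate disease and symptom onset within 5 days (8.1).

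The change in the WHO Clinical Progression Scale is listed in 1.0 and 3.0 with no time point, and 19.1 supplies none.

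**The concern.** Dosing covers Days 1 to 14, and Day 42 falls four weeks later. In a mild or moderate outpatient illness, many subjects in both arms may be symptom-free by then. For a subject whose Day 42 score is zero, Day 42 minus Day 1 is exactly minus the Day 1 score. The more subjects this describes, the more the Wilcoxon test ranks people by how ill they were at entry, which randomisation makes similar on average across arms. A real difference in the first two weeks would leave little trace.

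Section 19.1 says the estimates are meant to help plan later comparative trials. A near-null change score beside a favourable resolution curve would be awkward to interpret, and would be a poor effect size to carry forward.

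The WHO item has a related gap. If it were read only at Day 42, a subject who was admitted early and had recovered by then would look like one who never progressed, while section 2.1 names preventing progression as the ultimate goal.

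**Working it through.** **The plan's own figure.** The only sizing figure is the standard error of a safety proportion (19.2): sqrt(0.5 × 0.5 / 20) = 0.112, which agrees with the stated 11 percentage points. Nothing is sized for symptoms.

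**Inputs from the documents.** 30 subjects (7.1), 2:1 allocation (19.1), 20 on melatonin (19.2), hence 10 on placebo; 14 days of dosing; daily ratings to Day 42; two-sided 0.05. Gap from end of dosing to Day 42: 42 − 14 = 28 days.

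**Assumptions, not in the documents.** Exponential time to resolution; placebo median 7 to 21 days; a drug that halves the median (resolution-rate ratio 2).

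**Step 1: who is still unresolved at Day 42?** S(t) = exp(−ln 2 × t / median), with t = 41 days after Day 1.

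| Medians, placebo v melatonin (days) | Unresolved, placebo | Unresolved, melatonin | Expected subjects of 30 |
|---|---|---|---|
| 10 v 5 | 5.8% | 0.3% | 10 × 0.058 + 20 × 0.003 = 0.6 |
| 14 v 7 | 13.1% | 1.7% | 10 × 0.131 + 20 × 0.017 = 1.7 |
| 21 v 10.5 | 25.8% | 6.7% | 10 × 0.258 + 20 × 0.067 = 3.9 |

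For 10 v 5, the gap between arms is 5.5 points at Day 42. At Day 14 (t = 13) it is 41% − 17% = 24 points.

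**Step 2: how far does the Day 42 change reflect baseline?** In simulation with no treatment effect, with a score of zero once resolved and 60% of baseline until then, the mean correlation between the Day 42 change and minus the Day 1 score is 0.98 for a 7-day median, 0.93 for 10, 0.85 for 14 and 0.74 for 21.

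**Step 3: power of the unadjusted Wilcoxon test on change from Day 1, drug halving the median.** The first three rows use 1,500 simulated trials per case, a linear decline to resolution, Day 1 scores uniform on 4 to 15 and multiplicative noise of SD 0.3 on the log scale. The last four add independent noise to the Day 1 score.

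| Model | Placebo median (days) | Day 42 | Day 14 | Mean of Days 2-14 |
|---|---|---|---|---|
| Linear decline | 8 | 4.7% | 9.6% | 19.0% |
| | 10 | 5.8% | 11.8% | 22.5% |
| | 14 | 4.7% | 16.7% | 23.9% |
| With noise on Day 1 score | 8 | 4.5% | 7.6% | 12.9% |
| | 10 | 4.9% | 10.3% | 15.8% |
| | 14 | 5.4% | 12.0% | 14.3% |
| | 21 | 6.1% | 15.7% | 14.9% |

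A further run over medians of 8 to 21 days gave 4-7% for the Day 42 change and 13-25% for the unadjusted Days 2-14 mean. The step model of Step 2 gives 4.5%, 4.7%, 7.6% and 9.9% for Day 42 at medians of 7, 10, 14 and 21 days. The range can therefore reach about 10% if recovery is slow.

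**Step 4: is the test still valid?** Yes. With no effect, rejection was 4.2-4.9% in the step model for Day 42, and 4.3-5.2% in the linear model across the change measures.

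**Step 5: what does the planned log-rank test offer?** If all 30 resolve, the Schoenfeld formula gives power = Φ(sqrt(30 × 2/3 × 1/3) × ln 2 − 1.96) = Φ(2.582 × 0.693 − 1.96) = Φ(−0.17) = 43%. Simulation from daily data censored at Day 42 gives about 33-39%, and up to 41% in one run. In the step model its null rejection was 5.4-7.3%, so part of that figure is slight inflation.

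**Step 6: what does adjustment add?** A rank-based ANCOVA of the Days 2-14 mean on treatment and the Day 1 score gives about 23-29% power under the same assumptions.

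**The case against.** The strongest reply is that symptoms already have a good analysis. Speed of resolution is named first in the same line, uses the daily ratings, and targets exactly the effect a drug that shortens illness would produce. Its power exceeds that of any score summary tried here. This stands: a reader might infer that the trial's symptom comparison as a whole rests on Day 42, or would miss a drug that halves symptom duration, and section 19.1 does not support that.

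Second, the Day 1 to Day 42 wording may describe the observation window and not a two-point difference. Section 12.1 uses the same span for daily collection, and 19.1 mentions neither a Day 42 test nor a change score. This also stands. On that reading, however, the score outcome has no defined summary among 41 post-baseline days, and one still has to be named in advance.

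Third, recovery by Day 42 is assumed. Section 4.1 says only that non-hospitalised patients may have a milder course, and section 21.1 anticipates 20% hospitalisation (0.20 × 30 = 6 subjects). That is a fair caution. But power remains about 6-10% with a 21-day median and a quarter of placebo subjects unresolved, so the conclusion does not need near-universal recovery.

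On the WHO scale, hospitalisation and mortality are separate endpoints, so an admission is not lost. Peak severity has no endpoint of its own.

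**Conclusion.** The point holds in a limited form. The numeric symptom outcome lacks a defined day or summary. On its most literal reading it would be measured 28 days after dosing ends, with power of about 4-7% (up to about 10% under a step model with slow recovery) against a halving of median resolution time. That rests on assumed recovery times and score shapes.

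A reader might go further and say that the comparison measures baseline severity instead of treatment. That is too strong: randomisation keeps the type I error near 5%, and the loss is one of sensitivity. Nor can the WHO outcome be called uninformative, because no time point is stated; the problem arises only if it is read at Day 42 alone.

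The effect is on one secondary score analysis in a 30-subject pilot whose primary aim is safety. Power is low for every symptom measure at this size, so the gain is a clearer and more useful estimate for planning, not a decisive test.

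**What to change.** Amend 1.0, 3.0 and 19.1 together:

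- Name time to symptom resolution (Kaplan-Meier, log-rank) as the lead symptom analysis.
- Define the numeric symptom outcome as the mean of the daily questionnaire scores over Days 2-14, compared between arms with adjustment for the Day 1 score, for example by rank-based ANCOVA. As the plan imputes nothing, say that the mean uses the days actually rated.
- Report scores at Days 28 and 42 descriptively, by arm.
- State the WHO scale summary, for example the worst score from Day 1 to Day 42, so that subjects who progressed and then recovered are counted.

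An area under the daily scores or a baseline-adjusted repeated-measures model would also serve for the score; what matters is that one is fixed before unblinding. The daily ratings and the follow-up to Day 42 are already planned, so the cost is wording. The small downside is that the score result would speak to late persistence of symptoms only descriptively.
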